#### 3.1.4.2 Missing Data

The impact of missing data on the analysis of primary effectiveness and safety objectives is expected to be small since the Kaplan-Meier method will be performed for the primary objectives. For subjects who are lost to follow-up, the time to event will be censored at the last contact date.

Analysis will be based on available cases. The reasons for study withdrawal will be documented. There are no plans for imputation of any missing data. However, we will compare differences in baseline characteristics between subjects with complete data and subjects with early exit. Also, if the primary objectives are met ( $p < 0.05$ ) at 3 years, with >

5 subjects exiting prior to the 3-year follow-up, a tipping point analysis will be conducted to assess sensitivity to missing data. Missing data is defined here as subjects with less than 3 years of followup.

Data will be sorted by ascending event times, and subjects who are censored prior to the 3-year visit are assigned an event time equal to the date of last contact (index ablation date). Then, for each observation:

- 1) If the observation is censored, set time = time + 1 and event = 1.
- 2) Apply the logrank test (specified in section 3.2.1 or 3.2.2 for efficacy and safety, respectively) to find the new two-sided p-value and 95% loglog confidence interval.

The first observation where the confidence interval includes the performance goal (and the corresponding p-value  $\geq 0.05$ ) is the tipping point for the primary safety analysis. For either primary endpoint, if fewer than 5 subjects have missing data, a worst case analysis will be done instead of a tipping point analysis. This analysis will be performed in the mITT dataset.

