### 3.2.1.4 Sample Size Methods and Assumptions

[figure not shown]
Sample size was estimated using SAS v9.2 Proc Power. The sample size was calculated under an asymptotic z-test for a single binomial proportion with continuity adjustment under the following assumptions:

Power = 90%, Significance level = 0.025 (one-sided), Assumed underlying effectiveness rate = 55%, Performance goal = 45%.

Long-term (> 12 months) effectiveness of pulmonary vein isolation for treatment of atrial fibrillation (AF) ranges from 44-70%, with 40% reported as the minimum goal by physicians. Shah et al reported that the annual rate of atrial fibrillation recurrence after one year was 8.8% and Zou et al reported a similar annual rate of 7%. Based on the STOP AF results and assuming an annual rate of atrial fibrillation recurrence of 7%, the estimated effectiveness rate at 36 months would be approximately 55%. The performance goal of 45% was determined from the lower bound of 95% CI for the primary effectiveness rate in STOP AF study.

Figure 2 presents the sample size at different primary effectiveness rates under the assumptions outlined above.

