## 4 APPENDIX

### 4.1 Overall Sample Size

In order to adequately power for both the primary effectiveness and safety hypotheses, we require a sample size of 270 evaluable subjects to complete 36 months of follow-up. We estimate that the attrition rate will be approximately 10% per year for the duration of the originally intended 5 year follow-up period. Therefore, the final sample size required to achieve 270 subjects followed for 36 months and account for attrition (i.e. 10% per year) is 370 mITT subjects with procedure attempts. It is expected up to 400 subjects will need to be enrolled to ensure 370 mITT subjects with procedure attempts assuming a small number of subjects who are enrolled will not undergo a procedure.

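### The tipping-point rule for the 36-month effectiveness result converts dropouts only in the most lenient order, and the all-dropouts-fail bound is planned only when fewer than five subjects are missing

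*SAP*

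**What the plan says.** SAP 3.1.4.2 (Missing Data) first states that the impact of missing data "is expected to be small since the Kaplan-Meier method will be performed for the primary objectives". If a primary objective is met and more than five subjects exit before the 3-year visit, a tipping-point analysis follows. "Missing data is defined here as subjects with less than 3 years of followup".

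The procedure has three parts:
- Order: "Data will be sorted by ascending event times".
- Conversion: "If the observation is censored, set time = time + 1 and event = 1". The log-rank test and the 95% log-log interval are then recomputed.
- Stop: "The first observation where the confidence interval includes the performance goal" is the tipping point.

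The stopping sentence names only the safety analysis, but the recomputation step cites the methods of both primary objectives, so I read the rule as covering both. A first tipping observation makes sense only if conversions accumulate down the sorted list.

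The worst-case analysis is a fallback: "if fewer than 5 subjects have missing data, a worst case analysis will be done instead of a tipping point analysis". Section 4.1 plans for much more loss than that: "We estimate that the attrition rate will be approximately 10% per year". The sensitivity analysis in 4.4 concerns eligibility, not withdrawal.

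**The concern.** A tipping-point analysis asks how far the lost subjects would have to depart from the Kaplan-Meier assumption before the claim fails. The number depends on which of them are failed first. The plan fixes one order, and it is the order that gives the largest number. Later dropouts, whose conversion moves the 36-month estimate most, are not reached before the rule stops.

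This is the SAP's only sensitivity analysis of the primary effectiveness result for withdrawal. A reader of the final report would see a single count from the favourable end of the range, with no sign that other orders give fewer. At the planned attrition the reader would also not see what happens if every dropout is counted as a failure.

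**Working it through.** **Inputs from the SAP.** Effectiveness 55%, goal 45%, 90% power, one-sided 0.025 (3.2.1.4); Greenwood standard error with log-log 95% interval (3.2.1.3); 270 evaluable, 370 mITT, 10% attrition per year (4.1); 7% recurrence per year after year 1 (3.2.1.4).

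**Assumptions.** The 12-month freedom that leads to 55% at 36 months is not given. The 7% yearly rate implies 0.55/0.93² = 64% if multiplicative, or 55% + 2 × 7% = 69% if additive. No CTF is counted before day 90. Exits occur at a constant rate or, alternatively, at visit dates.

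**The plan's own figures.** For a one-sample z-test:

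n = [1.960·√(0.45·0.55) + 1.282·√(0.55·0.45)]² / 0.10² ≈ 260, rounded up to 261.

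With the continuity adjustment, (n/4)·[1 + √(1 + 2/(n·0.10))]² gives 270. For attrition, 270/0.9³ = 370.4. Both stated figures are reproduced.

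**Effect of one conversion.** Turning a subject censored at time t into a failure multiplies the 36-month estimate by 1 − 1/n(t), where n(t) is the number at risk. The other risk sets are essentially unchanged. At the planning inputs n(t) falls from 370 to 370 × 0.9³ × 0.55 ≈ 148 by month 36. The cost per conversion is therefore:
- earliest exits: 0.55/370 ≈ 0.15 percentage points;
- latest exits: 0.55/148 ≈ 0.37 percentage points.

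For any given number of conversions, ascending order leaves the point estimate highest. This does not depend on the assumptions above.

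**Tipping counts.** Cohorts of 370 were simulated, 300 per setting. Those with a lower limit above 45% and an estimate within one point of target were kept (about 70 to 105 per setting). The SAP's steps were applied cumulatively until the lower limit was at or below 45%. Mean counts:

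| 36-month freedom | Exit per year | 12-month freedom | Ascending | Random | Descending | Asc./desc. |
|---|---|---|---|---|---|---|
| 55% | 10% | 64% | 28.5 | 19.8 | 14.2 | 2.0 |
| 55% | 10% | 69% | 28.7 | 20.0 | 14.1 | 2.0 |
| 55%, exits at visits | 10% | 64% | 30.0 | 20.0 | 14.5 | 2.1 |
| 52% | 10% | 62% | 10.6 | 6.3 | 4.2 | 2.5 |
| 58% | 10% | 67% | 40.6 | 32.2 | 24.6 | 1.7 |
| 60% | 10% | 70% | 48.5 | 41.1 | 33.0 | 1.5 |
| 64% | 10% | 74% | 63.9 | 59.1 | 52.1 | 1.2 |
| 55% | 5% | 64% | 24.7 | 21.7 | 18.1 | 1.4 |

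In the first row about 70 subjects exit CTF-free, and ascending/random is 28.5/19.8 ≈ 1.4.

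**Failures beyond expectation.** Kaplan-Meier already implies that some dropouts fail after exit, mostly early ones. At 55%, 10% per year and 64% at 12 months, the roughly 28 ascending conversions exit at a median of about 5 months, and about 10.5 of them are already expected to fail. The 14 or so descending conversions exit at a median of about 31 months, with about 0.5 expected to fail. The excess needed to tip is about 17.6 ascending against 13.4 descending, and 17.6/13.4 ≈ 1.3. This ratio is bounded: the weight of one excess failure rises only from about 1/370 to 1/270, and 370/270 ≈ 1.37.

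**All dropouts failed.** Freedom then equals the chance of being both CTF-free and still followed: 0.55 × 0.9³ = 0.55 × 0.729 ≈ 40%, below the 45% goal.

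**The case against.** The best defence is that no single number of lost subjects must have failed; it depends on who they are. Latest-exit-first is an adversarial minimum. It makes subjects who were CTF-free at about 31 months all fail the next day, although recurrence is put at 7% per year. Ascending order starts with those who have the longest unobserved time and so the most room to fail. It also suits a rule shared with the 12-month safety endpoint, where latest-first would begin with exits after month 12 that cannot change the estimate.

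Much of this stands. A reader might infer that the plan overstates robustness two-fold. The documents do not support that as a general statement: two-fold is the gap to the smallest raw count at the planning inputs, and most of it reflects failures Kaplan-Meier already expects. A reader might also infer that a fragile success would be passed off as robust. Section 3.2 defines success by the two primary tests alone, and 3.1.4.2 sets no count that qualifies as robust. In a simulation with the CTF hazard doubled or tripled after exit, true freedom was 52.4% or 50.6% where Kaplan-Meier reports 55%, still above the goal.

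What does not fall away is that one order, the most lenient, is the only one reported. The plan's other steps on missing data, a baseline comparison of early exits with completers and a record of withdrawal reasons, do not supply the missing range.

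**Conclusion.** The point holds as a matter of one-sided reporting. The direction is exact for the Kaplan-Meier point estimate. The sizes hold at the SAP's planning inputs and rest on the assumed 12-month freedom and exit pattern. The gap between ascending and descending counts shrinks to about 1.3- to 1.7-fold at 58-60% observed freedom or 5% exit per year, is about 1.2-fold at 64%, and widens to about 2.5-fold at 52%, nearer the goal. The all-dropouts-fail bound cannot appear under the plan at anything like the expected attrition.

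The primary test is unaffected, and nothing here shows that the effectiveness claim itself is fragile. The sentence expecting a small impact because Kaplan-Meier is used is weak reasoning, since that method assumes exit is unrelated to outcome. It states an expectation only, and changing it is optional.

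**What to change.** In SAP 3.1.4.2, for the effectiveness endpoint:
- Report the tipping count in ascending order, in descending order, and as the median over many random orders. State the range rather than the ascending count alone, and do not rest the robustness statement on the descending count alone.
- Always report the estimate and interval with every CTF-free dropout counted as failed, whatever the number missing.
- Optionally, reword the sentence that expects a small impact because Kaplan-Meier is used.

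The cost is a short SAP edit and a few lines of code on data already held. The reported robustness figure becomes less favourable.

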### 3.1.5 Reports for which this Statistical Analysis Plan applies

This analysis plan applies to the study final report, and the analysis results may be reported in study-related publications and interim progress reports. Statistical analysis for study-related publications will not be limited to those defined in this plan.

## 3.2 Primary Objectives

The study will be considered a success if both primary effectiveness and safety objectives are met at one-sided 0.025 level of significance in the final analysis. The analysis will be conducted using all mITT subjects.

### 3.2.1 Primary Objective #1 (Primary Effectiveness Objective)

The primary effectiveness endpoint is the rate of subjects free of chronic treatment failure (CTF) at 36 Months.

#### 3.2.1.1 Hypothesis

The following hypothesis will be tested in a one-sided test at the 0.025 significance level.

Ho:  $P_e \leq 45\%$

Ha:  $P_e > 45\%$

where  $P_e$  is the probability of freedom from CTF at 36 months and 45% is the prespecified performance goal based on the lower bound of 95% CI for the primary effectiveness rate in the STOP AF study.

#### 3.2.1.2 Endpoint Definition

Chronic Treatment Failure is defined as:

- Documented atrial fibrillation lasting longer than 30 seconds (outside the 90 day blanking period) OR

- Intervention for atrial fibrillation (except for repeat cryoablation during the 90 day blanking period)

Intervention for atrial fibrillation is defined as: An invasive procedure intended for the definitive treatment of AF, including any ablation of the PVs or atrial triggers (other than protocol-specified ablation), interruption of AV nodal function, procedures to alter left atrial conduction or function such as the Maze procedure, or the implantation of an atrial pacemaker or atrial defibrillator; whether approved by relevant regulatory authorities or not for such indications; excluding electrical or pharmacologic cardioversion of rhythmias and excluding procedures solely directed at the treatment of atrial flutter or atrial tachycardias. A reablation permitted under Section 5.12 of the protocol is not an AF intervention.

### 3.2.1.3 Analysis Methods

#### A. Statistical Methodology

The Kaplan-Meier method will be used to estimate the probability of chronic treatment success at 36 months followup. The standard error will be approximated using Greenwood's formula. A two-sided 95% log-log confidence interval for the probability will be constructed. The Kaplan-Meier estimate and its 95% log-log confidence interval will be constructed from the day of protocol specified ablation procedure (Day 0) through the end of followup. For subjects with a treatment failure, the days of followup will be computed as the days from Day 0 to the failure date. For subjects without failure events, days of followup will be computed as the days from Day 0 through the last followup. For subjects who are lost to followup, the last contact date will be used as the last followup date.

The survival curve will be presented through 36 months. Note that the phrases 'at 36 months' and 'through 36 months as used throughout includes events from the 3 year visit, even when it occurs more than  $3 \times 365 = 1,095$  days from the start date. The 36 month visit may occur after 1,095 days since the visit window runs until 30 days past day 1,095. Rhythm monitoring that was initiated at the 36 month visit will be included in the analysis of the 36 month endpoint provided that the date of the documentation is no later than 30 days after the 36 month visit. Therefore, depending on the date of the 3 year visit, it is possible to include documentation as late as day 1,155. Not including such events after day 1,095 could underestimate the proportion at 3 years due to 36 month visits that occur after 1,095 days. This potential bias is addressed in the statistical analysis by considering the date of recurrence to be exactly 36 months from the study ablation procedure so that these events will be counted as CTF in the 36 month Kaplan-Meier analysis.

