### 2.2 Study Scope

The study is expected to enroll subjects over an 18 - 24 month period with post procedural follow-up consisting of clinic visits at 6 and 12 months, and 2 and 3 years. There was a CIP change in June of 2016 that reduced the follow up time of this study from 5 years to 3 years. Prior to sites' activation of version 6 of the CRF, some subjects may also have been seen at 4 year or 5 year visits. This data will be included in the summary of safety outcomes.

Since the primary endpoint of the study is assessed at 3 years, the power of the study is not affected by this change.

More than 30 investigational sites in the United States and Canada have participated in this investigation. The Principal Investigator is [name] at Northwestern Memorial Hospital in Chicago, Illinois.

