##### 3.1.2 Use of Adjudicated Data

For endpoint events that are to be adjudicated, only data fully adjudicated by the Adverse Event Adjudication Committee (AEAC) will be used in summaries and analyses. AEAC determination of Chronic Treatment Failure (CTF), Cryoablation Procedure Events (CPE), and Major Atrial Fibrillation Event (MAFE), and their respective onset dates, are what the endpoint analyses utilizing these events will be based on. For adverse events (AE) reporting, AEAC determination of seriousness, and relatedness status will be used. Note that for data freezes and analyses before the final report, it may not be possible for all data used to be adjudicated.

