### 3.3.2.3 Analysis Methods

#### A. Statistical Methodology

The Kaplan-Meier method will be used to estimate the probability of a subject being free of MAFE at 1, 2, and 3 year follow-ups. The standard error will be approximately using Greenwood's formula. Two-sided 95% log-log confidence intervals for the probability will be constructed for each of the five follow-ups. The Kaplan-Meier estimates and their 95% log-log confidence intervals will be constructed from the day of study specified cryoablation procedure (Day 0) through the end of each follow-up. For subjects with a MAFE, time until an event will be computed as the number of days from Day 0 to the onset date of the first MAFE. For subjects without a MAFE, the number of days at-risk will be computed as the days from Day 0 through the last time they had an opportunity to report a MAFE, which includes scheduled study follow-up visits and their associated testing plus the termination visit, if done. For subjects who are "lost to follow-up", time from Day 0 until last contact date will be used as the number of days at risk.

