### 4.3 Interim Subject Safety Monitoring

No formal interim analyses are planned. However, accumulating data for the safety endpoints may be analyzed at any time per regulatory agency's request. Hypothesis statistical testing will not be conducted until the final analysis. No alpha adjustment will be applied in terms of the analysis of the final primary endpoint for all subjects.

Note that incidence rate estimates from analyses for the interim reports may have some upward bias since subjects that recently had a 36-month visit that occurred prior to precisely 36 months will not be part of the risk set (denominator) at 36 months due to being censored at their last followup.

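### The 36-month effectiveness analysis moves late-visit failures to month 36 but censors event-free early attenders before it, a conservative bias that Section 4.3 admits only for interim reports

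*SAP*

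**What the plan says.** The primary effectiveness endpoint is freedom from chronic treatment failure (CTF) at 36 months, estimated by Kaplan-Meier with a log-log confidence interval and compared with a 45% performance goal (SAP 3.2.1).

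- **Failures.** Section 3.2.1.3 accepts documentation from the 36-month visit and its rhythm monitoring as late as day 1,155. It deals with failures after day 1,095 by "considering the date of recurrence to be exactly 36 months from the study ablation procedure so that these events will be counted as CTF".
- **Event-free subjects.** The same section says: "For subjects without failure events, days of followup will be computed as the days from Day 0 through the last followup". No rule carries an event-free early attender forward to day 1,095.
- **The admission.** Section 4.3 says that "incidence rate estimates from analyses for the interim reports may have some upward bias". The people it has in mind are "subjects that recently had a 36-month visit that occurred prior to precisely 36 months". Its explanation is that, in the Kaplan-Meier calculation, they "will not be part of the risk set (denominator) at 36 months due to being censored at their last followup".
- **Length of follow-up.** Section 2.2 reports the cut from 5 years to 3, and adds that "some subjects may also have been seen at 4 year or 5 year visits". The number is not given.
- **Dating of events.** Section 3.1.2 says of the adjudication committee's determinations: "and their respective onset dates, are what the endpoint analyses utilizing these events will be based on".
- **A different rule elsewhere.** For major atrial fibrillation events (MAFE), Section 3.3.2.3 defines the end of time at risk as the last opportunity to report an event, "which includes scheduled study follow-up visits and their associated testing plus the termination visit, if done". Last follow-up is not defined in this way for CTF.

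**The concern.** The SAP corrects one side of a visit-timing problem. Failures found at late visits are brought back to month 36 so that they count. Event-free subjects seen early are not carried forward to month 36, so they are missing from the denominator when those failures are entered. Failures found at early visits are also entered at their own dates, against a risk set that is already shrinking. Both features give too much weight to failures found at the visit.

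Section 4.3 describes the mechanism but treats it as a feature of interim data cuts, as if later contact would restore these subjects. Now that planned follow-up ends at 3 years, the 36-month visit is the last contact for anyone without a later one, and nothing restores them in the final report.

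At stake are the main effectiveness result of this post-approval study, which would be understated, and the power against the 45% goal.

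**Working it through.** **The plan's own figures.** With one-sided alpha 0.025, 90% power and 55% against 45% (3.2.1.4), n = [(1.960√(0.45×0.55) + 1.282√(0.55×0.45))/0.10]² = 260.06. The continuity adjustment, n/4 × (1 + √(1 + 2/(n×0.10)))², gives 269.97, so 270 as stated. With 10% attrition a year, 270/0.9³ = 370.4, against the stated 370 (4.1). The sample size is sound, but it takes no account of the dating rule.

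**Quantities the SAP does not give (assumed).** Let f be the share of 36-month visits held before day 1,095, taken as 25-75%. Let q be the share of subjects still at risk whose CTF is dated to that visit or its monitoring, taken as 1-7%. The upper value equals the 7% annual recurrence in 3.2.1.4.

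**Closed form.** Let N subjects be at risk just before the visits start. When a fraction x of the early attenders has been seen, about N(1 − fx) remain at risk, and the next slice dx yields q·f·N·dx failures. Over all early visits the added hazard is ∫ q·f/(1 − fx) dx = q × [−ln(1 − f)]. At day 1,095 the remaining N(1 − f) subjects contribute a further hazard of q. The correct total is about q, so the excess is q × [−ln(1 − f)], and freedom S falls by about S × q × [−ln(1 − f)]. For S = 55%, f = 50%, q = 3.5%: 0.55 × 0.035 × 0.693 = 0.0133, or 1.33 points.

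**Simulation.** 370 mITT subjects, 10% attrition a year, 7% annual recurrence after year 1, true freedom 55%, Kaplan-Meier at day 1,095, success if the lower log-log bound exceeds 45%. There were 3,000 runs per cell, with no later contact and no credit for time after the visit. At f = 50%:

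| q | Closed-form drop (points) | Estimated freedom | Power |
|---|---|---|---|
| 1% | 0.38 | 54.6% | 92% |
| 2% | 0.76 | 54.2% | 88% |
| 3.5% | 1.33 | 53.7% | 83% |
| 7% | 2.67 | 52.4% | 66% |

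Symmetric dating gives 55.0% and 94-95% power. The number at risk at day 1,095 is 75-80 under the SAP rule and 150-154 under symmetric dating.

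Across f, for q from 1% to 7%:

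| f | Drop in freedom (points) | Power | Power falls below 90% once q exceeds about |
|---|---|---|---|
| 25% | 0.2-1.1 | 94-87% | 4-4.5% |
| 50% | 0.4-2.6 | 92-66% | 1.5-1.75% |
| 75% | 0.8-5.0 | 86-29% | 0.5-0.6% |

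A second simulation, with pre-visit failures spread evenly over time, gave the same direction and similar size: at f = 50%, q = 3.5%, freedom 53.7% and power 81%; at q = 7%, 52.5% and 62%; symmetric dating about 93% power.

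**Variants at f = 50%, q = 1-7%.**
- 30% of subjects have a later visit: power 93-81%.
- 7 days of monitoring count as follow-up: 93-78%.
- 30 days count, with early visits within 30 days of day 1,095: no loss.
- Early visits spread over 14 to 90 days before day 1,095 (q = 3.5%): 53.7-53.8% and 83-84% power, so the early window edge, which the SAP does not give, hardly matters when follow-up ends at the visit.

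**Type I error.** At a true 45%, the success rate under the SAP rule is 0.1-2.2%, below the nominal 2.5%.

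**Tipping point.** Section 3.1.4.2 describes missingness in two ways: censoring before the 3-year visit, which leaves out early completers, and having under 3 years of follow-up, which includes them. Applying its algorithm to 600 simulated successful trials (f = 50%; q = 1, 3.5 and 7%), the tipping point never reached an early completer. The mean number of flips was identical under both definitions (25.4, 23.7 and 19.4). This is a wording point only.

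**The case against.** The strongest reply is that last follow-up is undefined for CTF. Since 3.2.1.3 admits monitoring documented up to 30 days after the visit, one could count that monitoring as follow-up. With 14 days counted, power at f = 50% is 92% (q = 3.5%) or 88% (q = 7%); with 30 days there is no loss. It is also fair that:

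- Section 4.3 speaks of subjects seen recently, which suits an interim cut, and it is silent on the final report.
- Some subjects had 4- or 5-year visits. If 60% had later contact, power is 92% even at f = 50%, q = 7%.
- Because adjudicated onset dates are used, q may be well below 7%. That value would put a whole year's recurrences at the visit.
- Censoring at last observation is standard, and carrying subjects forward credits unobserved time.

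Much of this stands as a limit on size. The 29% power figure needs the most adverse values of everything at once. With q at 1-2% and f up to 50%, the loss is 0.2-0.8 points and power about 88-94%.

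It does not remove the defect. Section 4.3 gives the SAP's own reading: these subjects are censored at last follow-up and leave the 36-month risk set. Nothing in the SAP reverses this for the final report when there is no later contact. Ordinary censoring would be harmless here if failures also kept their actual dates; the bias comes from re-dating one side only.

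**Conclusion.** The concern holds. As written, 3.2.1.3 treats failures and event-free subjects differently around day 1,095, and the resulting bias remains in the final primary analysis for every early attender without later contact. The direction is certain: CTF is overstated and 36-month freedom understated. Power can fall, type I error is not inflated, and no false success can result.

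The size is not certain, because the SAP gives neither the share of early visits nor the share of failures dated to the visit. Under the assumptions above (true 55%, no later contact, no credit after the visit) the drop runs from 0.2 to 5.0 points. Below the break-even values of q the loss is minor. This should be fixed: the bias is avoidable and sits in the main reported estimate, but it does not threaten the validity of a positive result.

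**What to change.** - **3.2.1.3:** state that a subject who completes the 36-month visit and its rhythm monitoring without CTF is event-free and at risk through day 1,095, even if the visit was early. Report the analysis by actual dates as a sensitivity analysis.
- **4.3:** do not limit the caveat to interim reports.
- **3.1.4.2:** for consistency, define missing as not having completed the 36-month visit.

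The cost is SAP wording and one derivation rule, with no new data. The downside is that up to a few unobserved weeks are credited as event-free for early attenders; the sensitivity analysis shows how much this matters.
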